11.4 LONGITUDINAL COMMUNITY STRUCTURE AND GENE EXPRESSION ANALYSIS

11.4.1 Sample Processing and DNA Extraction

For Aim 3, fecal samples from each child will be collected by the caregivers into sterile, screw-capped tubes containing RNA*Later* and frozen within 24 hours of collection in a home freezer. The participants will be instructed on how to collect the samples using protocols from the [name] laboratory and be provided with written, illustrated instructions. The research staff will review these instructions with the caregivers during enrollment (Appendix, IND protocol). Immediately after collection and freezing, a member of the research team will be alerted to retrieve the samples and transport them to the laboratory. The stool will be stored at -40°C until transport to the University of Maryland. All research staff will receive certification on handling procedures.

Stool samples will be thawed on ice to remove representative 1 gram samples for DNA and RNA extraction as previously described.[109] These methods provide high quality nucleic acids for microbiome analysis on the Illumina sequencing platforms (see below).

11.4.2 Microbiome Community Profiling

16S rRNA gene amplification, sequencing and raw 16S rRNA data processing: The gut microbiota will be characterized by sequencing bacterial 16S rRNA gene amplicons from stool samples. A region of ~469 bp encompassing the 16S V3-V4 hypervariable regions[110-113] will

be targeted for sequencing using MiSeq's 300 bp paired-end sequencing reads and the two universal PCR primers 319F and 806R,[114] according to procedures previously published at The Institute for Genome Sciences (IGS) at the University of Maryland School of Medicine.[115, 116] Barcoding[114] will be used to multiplex >400 samples per MiSeq run, which will provide a sampling depth (~20,000 read pairs) sufficient to characterize the microbiota with high resolution. Raw 16S rRNA reads will be processed using published protocols.[114, 117, 118] Within- (alpha-diversity) and between- (beta-diversity) sample comparisons will then be performed using QIIME.[119] Enterotype classification will be carried out using the methods of Arumugan[120], as modified by the [name] laboratory.

Microbiota will be compared cross-sectionally and longitudinally, using parameters such as diversity and evenness (Shannon, Simpson index), and similarity (phylogenetic UniFrac distance, Jensen-Shannon divergence), determined using standard tools, such as Mothur,[121] QIIME,[119] and statistical R package (www.r-project.org). In addition, statistically significant correlations between specific microbiota members and post-BB-12 time points, subject clusters, and clinical outcomes will be determined using bioinformatics tools, such as eLSA,[122] Metastats,[123] and LEfSe.[124] Since there is no universal standard for such correlations, we will use all existing statistical tools developed to analyze 16S rRNA gene datasets. We will incorporate in our analysis any new statistical tool developed during the course of the study by either IGS researchers or external laboratories. The 16S dataset will also be used to simulate microbiota functional compositions using PiCRUSt,[125] which uses available genome sequence data to infer functional gene contents based on the 16S rRNA microbiota compositions. This method will provide an alternative access to functional microbiota characterizations.

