7.2 INCLUSION CRITERIA

We will enroll 300 participants, half for the BB-12 yogurt drink and half for the control yogurt. All parents of children 3-12 prescribed a penicillin or cephalosporin class antibiotic for a respiratory infection will be alerted of the study by their physician or by the study team.

Inclusion: Participants will be eligible if:

- 1. Child is between ages of 3-12
- 2. Caregiver has the ability to read, speak and write English or Spanish
- 3. Household has refrigerator for proper storage of drink
- 4. Household has telephone access
- 5. Enrollment must take place within 24 hours of starting antibiotics
- 6. Outpatient treated
- 7. Treatment with a penicillin or cephalosporin class antibiotic regimen for 7-10 days for a respiratory infection; the following is a list of inclusive antibiotics:
 - a) Amoxicillin
 - b) Augmentin (amoxicillin/clavulanate)
 - c) Ancef (cefazolin)
 - d) Cefadroxil
 - e) Cephalexin
 - f) Cephradine
 - g) Duricef (cefadroxil)
 - h) Keflex (cephalexin)
 - i) Kefzol (cefazolin)
 - j) Velosef (cephradine)
 - k) Ceclor (cefaclor)
 - I) Cefotan
 - m) Cefoxitin
 - n) Ceftin (cefuroxime)
 - o) Cefzil (cefprozil)
 - p) Lorabid (loracarbef)
 - q) Mefoxin (Cefoxitin)
 - r) Zinacef (cefuroxime)
 - s) Omnicef (cefdinir)
 - t) Suprax (cefixime)
 - u) Dicloxacillin
 - v) Pen-Vee K (penicillin)

A respiratory infection will be classified as any infection the physician designates as strep or non-strep pharyngitis, otitis media, pneumonia, sinusitis or bronchitis that results in a prescription of antibiotics.

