For Aim 2, numerous exploratory techniques (i.e., all descriptive statistics previously mentioned) will be performed to verify that the probiotic is safe and well tolerated. Additionally, the AEs will be collected and studied over time of enrollment. The rates of AEs will be estimated, 95% confidence interval be constructed for describing precision and statistically compared between groups. This will be accomplished using parametric or nonparametric tests. Further, in order to accurately identify patient populations or subgroups that can benefit from the BB-12 probiotic, decision tree models will be examined. Using decision trees, we may be able to identify groups of subjects that have no AEs versus those with an AE. Similarly, cluster analyses may also be employed to identify potential pockets of subjects that share similar characteristics but differ with respect to AEs. This is related to an area known as "unsupervised" modeling in data mining, but is appropriate in this Phase II trial for finding subgroups of subjects that have plausible similarities and also differences.

Statistical analysis will be performed using the intention to treat principle; all subjects enrolled and randomized will be accounted for in the final analysis in their randomized group. One interim analysis will be performed when approximately 50% of the subjects have been recruited. While the alpha for stopping the trial will be set at 0.01, it is unlikely that we would want to stop this trial at that point even if significance is achieved, but the Data Safety Monitoring Board, PI and NIH representative will make that final decision. For Aim 1, the level of significance for the primary objective will be tested at alpha = 0.029 to account for the one interim analysis.

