11.4.3 Anticipated Results and Interpretation

The experiments described in this aim will provide us with sequential samples from which data on both microbial composition (based of 16S rRNA profiling) and community function (based on RNASeq data) can be generated. We anticipate that longitudinal 16S rRNA profiling will provide insight into a number of distinct shifts in the microbiota (i.e., loss of particular taxa, loss of overall community diversity) that reflect the impact of antibiotics (control group) and antibiotics plus BB-12 (active yogurt group).

The impact of antibiotic treatment on the microbiota: In this clinical trial, all participants will be treated with a 7-10-day course of antibiotics beginning on day 1, and will be followed for another 20-23 days following cessation of antibiotic therapy. We will assess changes in the microbiota at five time points over this 30-day period. This study design will provide us an opportunity to capture information on antibiotic-induced changes in the microbiota, as well as monitor the recovery of the microbiota in 300 participants. We anticipate that a subset of participants will develop diarrhea, and we will generate data on microbiota changes during the progression from the diarrheal state to the non-diarrheal state. This will allow us to ask if changes in the relative abundance of specific members of the gut microbiota (either alone or in combination) correlate with clinical outcome. To our knowledge, there have been no studies that examine the microbiota during the progression to a diarrheal state and the resolution of the diarrheal state. There have been limited studies on the treatment with antibiotics,[47, 126] but not in the context of disease resolution, nor in a pediatric population. We anticipate these findings will be novel and provide insight into the dynamics of the human gastrointestinal tract.

We will also use the baseline16S rRNA data to identify gut enterotypes in the 300 participants in this clinical trial. With regard to this aspect of data analysis, we will test the hypothesis that specific enterotypes are more/less resistant to development of antibiotic-induced diarrhea and more/less likely to show complete recovery of community structure following antibiotic

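### Section 11.4.2 plans significance tests of taxa against undefined subject clusters; if these are the 16S-derived enterotypes, those p-values are circular

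*Combined protocol and SAP*

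**What the plan says.** Objective 3 (section 5.1.2) is a secondary objective covering microbiota structure and gene expression. Under it, section 11.4.2 says that "statistically significant correlations between specific microbiota members and post-BB-12 time points, subject clusters, and clinical outcomes will be determined using bioinformatics tools". It names eLSA, Metastats and LEfSe as examples and then opens the choice to every existing tool for 16S data.

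The paragraph before that sentence says "Enterotype classification will be carried out using the methods of" a cited paper, as modified by a named laboratory. Section 11.4.3 gives the data source: "We will also use the baseline16S rRNA data to identify gut enterotypes in the 300 participants". It then sets out a hypothesis that "specific enterotypes are more/less resistant to development of antibiotic-induced diarrhea".

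Two other places could supply clusters of subjects. Section 11.3 says for Aim 2 that "cluster analyses may also be employed to identify potential pockets of subjects that share similar characteristics but differ with respect to AEs". Section 11.4.6 plans an unsupervised mixture-model integration of clinical outcomes, 16S data and gene expression.

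The term *subject clusters* is not defined. The plan does not say which of the five stools is tested against the clusters, and it does not limit taxon differences between clusters to description.

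**The concern.** A test of one taxon across groups takes its null distribution from labels that were set without reference to that taxon's abundance. Enterotype labels are chosen so that children within a group have similar taxon profiles and children in different groups have dissimilar ones. The hypothesis that the labels are unrelated to a major taxon is then false by construction, whether or not distinct enterotypes exist. A small p-value shows that the algorithm split the children on that taxon. It does not show that the split is real, or that the taxon marks a biological type.

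This is separate from multiplicity and from repeated stools per child. It arises with one taxon, one tool and one stool.

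At stake is a list of significant enterotype-associated taxa that could be read as support for enterotypes in this sample. Sections 11.4.3 and 11.4.5 raise enterotypes as a possible explanation of resistance to diarrhea, recovery of the microbiota and response to BB-12.

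**Working it through.** **Stated figure.** There is none to reproduce. For Aim 3 the plan gives no significance level, number of taxa, number of clusters or error rate.

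**Inputs from the plan.** 300 children (section 7.2: "We will enroll 300 participants, half for the BB-12 yogurt drink and half for the control yogurt"), about 20,000 read pairs per sample, and Jensen-Shannon divergence as one listed similarity measure (both section 11.4.2).

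**Assumptions, because the plan does not give them.** 30 or 100 taxa, with mean abundance proportional to 1/rank^1.2. Two or three clusters, formed by k-medoids on root Jensen-Shannon divergence. A Kruskal-Wallis test at 0.05 as a stand-in for any test that treats the labels as fixed. *Major taxa* means the ten most abundant. 40 replicates per setting.

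**Step 1: generate data with no clusters.** Every child is drawn from one population under one of three abundance models (Dirichlet, independent log-normal, correlated log-normal). Reads are multinomial with 20,000 draws.

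**Step 2: cluster, then test on the same stool.** For profiles P and Q with M = (P+Q)/2, the distance is √[½KL(P‖M) + ½KL(Q‖M)]. Each child goes to the nearest medoid. For each taxon, H = 12/[N(N+1)] · Σ n_k(R̄_k − (N+1)/2)², with N = 300 (tie-corrected in practice), is referred to χ² with k−1 degrees of freedom.

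Mean share of the ten major taxa with p<0.05, with the share after Benjamini-Hochberg control in brackets:

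| Abundance model | Taxa | 2 clusters | 3 clusters |
|---|---|---|---|
| Dirichlet, concentration 20 | 30 | 66% (58%) | 81% (77%) |
| Dirichlet, concentration 20 | 100 | 63% (50%) | 84% (68%) |
| Log-normal, independent | 30 | 72% (69%) | 92% (91%) |
| Log-normal, independent | 100 | 70% (64%) | 85% (81%) |
| Log-normal, correlated | 30 | 77% (75%) | 94% (94%) |
| Log-normal, correlated | 100 | 79% (78%) | 96% (96%) |

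Varying the Dirichlet concentration (30 taxa) gave 58% and 72% at 5, 65% and 79% at 20, and 56% and 73% at 50, for two and three clusters. The overall range of means is therefore 56–96%. Of ten major taxa, that is 10 × 0.56 = 5.6 to 10 × 0.96 = 9.6 significant, against 10 × 0.05 = 0.5 at the nominal rate.

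In the Dirichlet sensitivity runs, single replicates ranged from 20% to 100%. Over all taxa, rare ones included, the mean share across the table's settings was 16–92%, so the statement about most taxa holds for major taxa only.

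**Step 3: isolate the cause.** Permuting the same labels gave 4.5–6.5% over all taxa. Random external labels gave 4.2% of the ten major taxa. The excess comes from deriving the labels from the tested data.

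**Step 4: other ways out.** Leaving the tested taxon out of the clustering still rejected 61% (five most abundant taxa, three clusters, abundances as proportions). For baseline clusters tested on a later stool (log-normal, 30 taxa, three clusters), the result depends on the within-child correlation of taxa:

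| Within-child correlation | Major taxa with p<0.05 |
|---|---|
| 0 | 4% |
| 0.3 | 34% |
| 0.6 | 61% |

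**Second simulation.** With 60 taxa, separate between-child and within-child variation and 150 trials per setting, the shares were 57–66% for two clusters and 73–82% for three. Permuted labels gave 4–6%.

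**The case against.** The strongest reply is that the premise is an inference. Section 11.4.2 uses *enterotype* in one paragraph and *subject clusters* in the next and does not link them. If the clusters are groups sharing clinical characteristics (section 11.3), the circularity does not arise. This stands, and it is why the point is conditional. It does not settle the matter, because the section 11.3 clustering is optional, belongs to Aim 2, and is not referred to in section 11.4.2. Clusters from section 11.4.6 would still be built partly from 16S data.

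Second, the tested stool is not stated. If baseline clusters were tested only on later stools, the inflation could be small. This also stands, but section 11.4.2 makes both cross-sectional and longitudinal comparisons and states no such restriction.

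Third, a reader might infer that the enterotypes are never shown to exist. The documents do not support that. The method lies in a cited paper with a laboratory's modification, and what it does about cluster number, cluster strength or external reference groups cannot be seen.

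Fourth, a reader might infer that the enterotype analysis of diarrhea is invalid. It is not: diarrhea is not used to form baseline 16S enterotypes, and a data-derived grouping can be tested against an outside outcome without being a natural type. Nor do sections 11.4.3 and 11.4.5 cite taxon-by-cluster p-values as evidence for that hypothesis.

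Finally, rejection here is not a type I error for the hypothesis that the labels are unrelated to the taxon, since that hypothesis is false by construction. It misleads only when read as evidence of real clusters or their markers.

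**Conclusion.** The point holds conditionally. The plan commits to significance tests of taxa against groups it does not define. On the most natural reading of section 11.4.2 with 11.4.3, those groups are built from the same children's 16S profiles. In that case the p-values are uninformative about whether the taxa mark real groups. With clustering and testing on one stool and no true clusters, 56–96% of the ten major taxa were significant on average (50–96% after false-discovery control), against about 5% with independent labels. For a later stool the range was 4–61%.

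The sizes rest on assumed taxa, cluster numbers, abundance models, clustering algorithm and test. In every same-sample setting tried, the mean exceeded half of the major taxa. It would go too far to say that Aim 3 will report enterotype-associated taxa whatever the data, because the definition of the clusters and the tested stool are both open.

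The harm is confined to one of the three targets in the quoted sentence, within a secondary objective. The primary comparison of diarrhea between arms is not touched.

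**What to change.** In section 11.4.2:

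- Define *subject clusters*: the data they are formed from, and the stool or stools used.
- Where they derive wholly or partly from 16S data, remove them from the list of significance tests of microbiota members. Describe the defining taxa (for example by medians or loadings) without p-values.
- Keep p-values for associations between cluster membership fixed at baseline and variables not used to form the clusters, such as study arm, diarrhea and adverse events. For groups from the section 11.4.6 integration, this excludes any clinical outcome entered in the model.
- If clusters formed only from clinical characteristics are meant, say so; the tests can then stay.

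An optional addition is to compare a cluster-strength statistic, such as the silhouette, with its distribution in data simulated from a fitted single population. No inference specified in the plan depends on it.

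The cost is a change of wording, plus one simulation if the optional check is adopted. No new samples are needed. The downside is fewer significant taxa to report.

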11.4.3 Anticipated Results and Interpretation

The experiments described in this aim will provide us with sequential samples from which data on both microbial composition (based of 16S rRNA profiling) and community function (based on RNASeq data) can be generated. We anticipate that longitudinal 16S rRNA profiling will provide insight into a number of distinct shifts in the microbiota (i.e., loss of particular taxa, loss of overall community diversity) that reflect the impact of antibiotics (control group) and antibiotics plus BB-12 (active yogurt group).

The impact of antibiotic treatment on the microbiota: In this clinical trial, all participants will be treated with a 7-10-day course of antibiotics beginning on day 1, and will be followed for another 20-23 days following cessation of antibiotic therapy. We will assess changes in the microbiota at five time points over this 30-day period. This study design will provide us an opportunity to capture information on antibiotic-induced changes in the microbiota, as well as monitor the recovery of the microbiota in 300 participants. We anticipate that a subset of participants will develop diarrhea, and we will generate data on microbiota changes during the progression from the diarrheal state to the non-diarrheal state. This will allow us to ask if changes in the relative abundance of specific members of the gut microbiota (either alone or in combination) correlate with clinical outcome. To our knowledge, there have been no studies that examine the microbiota during the progression to a diarrheal state and the resolution of the diarrheal state. There have been limited studies on the treatment with antibiotics,[47, 126] but not in the context of disease resolution, nor in a pediatric population. We anticipate these findings will be novel and provide insight into the dynamics of the human gastrointestinal tract.

We will also use the baseline16S rRNA data to identify gut enterotypes in the 300 participants in this clinical trial. With regard to this aspect of data analysis, we will test the hypothesis that specific enterotypes are more/less resistant to development of antibiotic-induced diarrhea and more/less likely to show complete recovery of community structure following antibiotic

perturbation. To our knowledge, the impact of antibiotics on the gut microbiota has not been evaluated in the context of gut enterotypes and this will likely provide novel insights into differences in the stability of gut communities.

The impact of BB-12-supplemented yogurt on the microbiota: In addition to the observation of antibiotic-induced changes in the gut microbiota, we will also be able to examine the impact of concomitant administration of BB-12-supplemented yogurt over time in half of the participants. We will specifically look for differences between the control and active yogurt groups with regard to the degree of antibiotic-induced disturbance of the microbiota (i.e., loss of particular taxa, loss of overall community diversity) as well as the extent and time course of recovery of the microbiota following cessation of antibiotic therapy. It has been suggested that probiotics help to speed the recovery of the microbiota following antibiotic administration,[127] and this clinical trial will generate a significant amount of data to help to support or refute that assertion.

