4.3.2 Known Potential Benefits

BB-12: *Bifidobacterium lactis* strain BB-12 is a commercially available probiotic strain used in a number of feeding and clinical trials. Such supplements have shown potential benefits in treatment and prevention of varied diseases including diarrhea, asthma, necrotizing enterocolitis and allergies. It has been also found to significantly improve skin conditions in eczema patients.

Yogurt: Yogurt has its own known benefits coming from milk. For every 6-ounce of serving, there are about 9 grams of animal protein, plus several other nutrients found in dairy foods, like calcium, vitamin B-2, B-12, potassium, and magnesium. Furthermore, yogurt with active cultures is found to help certain gastrointestinal conditions including, lactose intolerance, constipation, and diarrhea.

Yogurt, which is more readily available and accepted by general public, has the potential to greatly influence health if efficacious probiotic dosages and species are available in the product. Therefore, we believe that the benefits of the BB-12 supplemented yogurt far outweigh the discomfort and small risks participants might experience.

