5 OBJECTIVES/STATISTICAL METHODS

5.1 Study Objectives

5.1.1 Primary Objective

Objective 1: To test the efficacy of high dose BB-12 supplemented yogurt in preventing AAD, compared to yogurt without BB-12, in children receiving antibiotics.

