6 STUDY DESIGN

This is a randomized, single center, Phase 2 study to test the efficacy of *Bifidobacterium animalis* subsp. *lactis* (*B. lactis*) strain BB-12 (BB-12) yogurt in preventing AAD, compared to yogurt without BB-12, in children receiving antibiotics for a respiratory infection. Three hundred participants will be randomized to two groups, BB-12 supplemented yogurt and control yogurt, using the random allocation rule. This randomization approach will ensure equal allocation of subjects to each group. Participants will be recruited through Capital Area Primary Care Research Network (CAPRICORN), a practice-based research network (PBRN). Children prescribed a 7-10-day penicillin or cephalosporin class antibiotic for a respiratory infection, who meet all the inclusion and exclusion criteria will be enrolled. There will be no exclusion based on race, gender, or insurance status. Based on our previous experience with clinical trials, we will be able to enroll 75 participants in the first year.

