7.4 RANDOMIZATION

The randomization scheme will be generated using permuted blocks of varying size. It will be impossible for research personnel involved with participants to adjust randomization or discern what drinks participants were receiving, ensuring true allocation concealment. Participants who receive the control product will receive all identical interventions (i.e. stool collection, follow-up, etc.) that the active group receives.

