8.1.3 Yogurt Drink Manufacture

Yogurt drink manufacture is broken into two major activities, 1) preparation of the yogurt and 2) blending with other ingredients to prepare the drink. To make the yogurt, a yogurt base is formulated to contain 9.0% milk solids non-fat (MSNF), 1.3% fat and 3.0% sugar using skim milk, cream, non-fat dry milk and sugar. The wet ingredients (skim milk and cream) are mixed together and then blended with previously weighed dry ingredients (sugar and non-fat dried milk). After blending the yogurt mix is pasteurized and homogenized (2000 psi first stage, 500 psi second stage) at 83°C for 29 sec. The pasteurized, homogenized mix is pumped to fermentation tank and given an additional heat treatment of 85°C for 30 min to denature whey proteins, then cooled to 42°C prior to inoculation with 0.02% of the yogurt starter culture (YFL-

720). The inoculated mix is agitated for 15 minutes and then allowed to incubate quiescently until the pH reaches 4.6.

To prepare the yogurt drink the gel structure of the fermented yogurt is disrupted by agitation and blended with a mixture of pectin, 36 DE corn syrup solids, sugar and water. The pectin-containing mixture is prepared by heating water, sugar, 36DE corn syrup solids, and pectin to 80°C, holding for 1 hour. This mixture is then cooled to 40°C and added to the fermented white mass resulting in the unflavored yogurt drink base. To flavor the product, strawberry puree is then added to the yogurt drink. The composition of the yogurt drink is shown in Table 4 and the ingredients used in manufacture are listed in Table 5. At this point, a portion of the yogurt drink is homogenized (1500 psi first stage, 500 psi second stage) for a second time to create a drinkable consistency and packaged in plastic bottles. To prepare the yogurt drink containing BB12, an appropriate amount of (BB-12) is added to the yogurt drink, allowed to mix for 15 minutes and then homogenized and packaged as describe above. The packaged yogurt is stored at 4°C.

Table 4. Composition of Strawberry Yogurt Drink

Component	Composition in Yogurt Drink
Fat	1.0%
Milk Solids Non-Fat	6.8%
Sucrose	6.1%
Corn Syrup Solids	6.4%
Pectin	0.4%
Strawberry Puree	3.0%

Table 5. Ingredients for Strawberry Yogurt Drink

Component	Supplier	Specifications
Milk ¹	Land-O-Lakes	PMO^2
Nonfat Dry MilkSolids ³	Various approved vendors	COA ⁴
Granulated Sugar ³	Various approved vendors	COA
Corn Syrup Solids ³ (42 DE)	Various approved vendors	COA

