11.4.5 Anticipated Results and Interpretation

Gene expression and pathway reconstruction for the community: The metatranscriptomic studies will provide information about the gene expression profiles of all members of the microbiota as well as the *in vivo* expression profile for the probiotic, BB-12. Together, these data

will provide insight into (i) which organisms are metabolically active in the presence of antibiotic with and without BB-12; and (ii), whether the gene expression profile of BB-12 is similar in all patients. We anticipate that we will identify different transcriptional profiles that are associated with (i) administration of antibiotic alone or (ii) the concomitant administration of antibiotics and yogurt in subjects that either develop AAD or do not. What is not known is whether these transcriptional programs will differ depending on clinical outcome and/or the starting composition of the microbiota and/or the ingestion of BB-12. It is possible that each gut enterotype will exhibit a differential response to BB-12, in terms of changes in community composition, and/or gene expression. Such a finding will be of value in understanding the parameters that identify those subjects most likely to respond to probiotic intervention.

Antibiotic resistance gene expression profiles: With the increase in prevalence of antimicrobial resistance among bacterial pathogens and in environmental samples, investigators at IGS have developed bioinformatics pipelines for the identification of resistance genes in metagenomic/metatranscriptomic samples. The current iteration of the analysis pipeline identifies a total of 121 reference markers (representing 357 allelic variants) in the proposed reference database, based either on the screening of previously published literature or based on our own ongoing work in this field. Therefore, we have the ability to identify antibiotic-induced increases in resistance gene expression in the metatranscriptomics dataset and we will include this information as part of the analysis. Collectively, the work to be carried out as part of Aim 3 will provide the most robust description of metatranscriptome changes in association with concomitant antibiotic and probiotic administration to date.

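### Aim 3 treats the control arm as antibiotic only, although every child drinks yogurt, and it reads between-arm stool differences as recovery without separating BB-12's own reads

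*Combined protocol and SAP*

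**What the plan says.** **The comparison.** The primary objective in Section 5.1.1 tests BB-12 yogurt "compared to yogurt without BB-12, in children receiving antibiotics". Section 6 confirms it: "Three hundred participants will be randomized to two groups, BB-12 supplemented yogurt and control yogurt". There is no arm without yogurt.

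**The product.** Section 8.1.3 describes one starter-fermented drink. The milk mix receives its last heat treatment, is "then cooled to 42°C prior to inoculation with 0.02% of the yogurt starter culture", and ferments. No later heat step on the fermented mass is described. Adding BB-12 is the only described difference between the two drinks.

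**How Aim 3 reads the arms.** Section 11.4.3 expects shifts that "reflect the impact of antibiotics (control group) and antibiotics plus BB-12 (active yogurt group"). Section 11.4.5 anticipates different transcriptional profiles for "administration of antibiotic alone or (ii) the concomitant administration of antibiotics and yogurt".

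**How Aim 3 reads differences between arms.** Section 11.4.3 will compare the groups on "the degree of antibiotic-induced disturbance of the microbiota" and on the extent and timing of recovery. It presents the result as evidence on whether probiotics speed recovery. Section 11.4.2 lists Shannon and Simpson indices, UniFrac, Jensen-Shannon divergence, Metastats and LEfSe. It has no step that sets aside or separately reports the swallowed organism.

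**BB-12 in stool.** Section 4.1.4 reports survival through the gut and persistence for 1-3 weeks after feeding. Section 8.5 uses B. lactis PCR on baseline and Day 7 stool to assess compliance.

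**The concern.** Two readings go further than the design allows.

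1. **Control arm.** A contrast of antibiotic alone with antibiotic plus yogurt has no children in its first category. Yogurt and antibiotic run together and stop at about the same time (Days 7-10), so control-arm change from Day 7 to Day 14 mixes stopping the antibiotic with stopping a daily yogurt. The protocol does not treat yogurt as inert. Section 4.3.2 says "yogurt with active cultures is found to help certain gastrointestinal conditions including, lactose intolerance, constipation, and diarrhea".
2. **Between-arm differences.** Only the active arm swallows BB-12. Its DNA enters the diversity, distance and taxon comparisons as though it were a change in the child's own community. A difference could be recovery, product passing through, or both, and the plan has no analysis to tell them apart.

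At stake are two conclusions that a report of Aim 3 might draw: what antibiotics alone do to the gut community, and whether BB-12 speeds its recovery.

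**Working it through.** **1. Who receives what.** By Sections 5.1.1 and 6, with 1:1 allocation in Section 11.2, 150 children receive antibiotic plus control yogurt and 150 receive antibiotic plus BB-12 yogurt. Antibiotic-only children number 0. The base drink is common to both arms, so it cancels in the randomized contrast. It does not cancel in change over time within the control arm.

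**2. Which samples can carry BB-12.** The plan's own figure comes first. Section 11.4.3 gives 20-23 days of follow-up after antibiotics end: 30 - 10 = 20 and 30 - 7 = 23, so it reproduces. Days from last yogurt to each nominal sampling day are:

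| Last dose | Day 7 | Day 14 | Day 21 | Day 30 |
|---|---|---|---|---|
| Day 7 | 0 | 7 | 14 | 23 |
| Day 8 | dosing | 6 | 13 | 22 |
| Day 9 | dosing | 5 | 12 | 21 |
| Day 10 | dosing | 4 | 11 | 20 |

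Against persistence of 7-21 days:
- Days 7 and 14 fall during dosing or within even the lower bound.
- Day 21 is reached only if persistence is at least 11-14 days.
- Day 30 is reached only if dosing ran to Day 9 or 10 and persistence is near its upper bound.

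Section 9.2 has yogurt for Days 1 through 7-10, while Section 8.2 also says ten consecutive days. These must be reconciled, because Day 30 depends on the last-dose date.

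**3. How large the product signal could be.** Inputs:
- Daily dose: at least 10^10 CFU (Section 8.1.2), up to 118.3 ml x 10^8.86 = 8.57 x 10^10 CFU (4 ounces at the highest mean count in Table 6).
- Gut community: 10^14 organisms (Section 4.1.1).
- Depth: about 20,000 read pairs (Section 11.4.2).
- Assumptions not in the documents: antibiotic depletion D of 1, 10 or 100-fold; resident Shannon index H of 2-3 (natural log); read share equal to cell share; BB-12 absent at baseline.

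Formulas, with h the binary entropy:
- Share: f = dose / (dose + 10^14/D)
- Shannon shift: h(f) - f x H, in natural logs
- Jensen-Shannon divergence from the same profile without BB-12: h(f/2) - h(f)/2, in bits; the distance is its square root

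| Depletion | Share f | Reads of 20,000 | Shannon shift | JS divergence | JS distance |
|---|---|---|---|---|---|
| none | 0.01-0.09% | 2-17 | 0.001-0.005 | 0.00005-0.0004 | 0.007-0.02 |
| 10-fold (assumed) | 0.1-0.85% | 20-170 | 0.005-0.03 | 0.0005-0.004 | 0.02-0.07 |
| 100-fold (assumed) | 1.0-7.9% | 198-1,579 | 0.03-0.12 | 0.005-0.04 | 0.07-0.20 |

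Example, top of the last row: f = 8.57 x 10^10 / (8.57 x 10^10 + 10^12) = 0.0789. With h(f) = 0.276 and H = 2, the Shannon shift is 0.276 - 0.158 = 0.118. The divergence is 0.041 and the distance 0.20.

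This is a crude bound: one day's dose against the whole gut, with no growth of BB-12. Taxon-level tests do not need a large share. Metastats or LEfSe can report B. lactis itself as a between-arm difference because only one arm swallows it.

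**The case against.** **The randomized contrast is sound, and the plan mostly states it correctly.** Sections 5.1.1 and 6 name the right comparator, and 11.4.5 speaks of antibiotic with and without BB-12 just before the faulty phrase. This stands. A reader might infer that both Aim 3 readings are simply wrong, and the documents do not support that. The control arm is mislabelled. The recovery reading is not cleanly identified, but it is not shown to be false, since part of any difference may be genuine recovery.

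**Objective 3 concerns fecal microbiota.** Section 5.1.2 does not restrict it to resident organisms, so the unfiltered profile answers the objective as written. This stands. Filtering serves the recovery interpretation in 11.4.3 and is not a correction of the objective.

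**The effect may be trivial.** On the protocol's own counts it is very small for Shannon and Jensen-Shannon measures, and a read share of several percent needs heavy assumed depletion or growth. This stands. Section 4.1.2 also says BB-12 can be native, so treating it as a new taxon is a worst case. Loss of particular taxa, one of the disturbance measures in 11.4.3, is not created by adding an organism.

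**Exposure is already measured.** Section 8.5 does B. lactis PCR and 11.4.5 examines BB-12 expression. Both help, but neither takes product reads out of the diversity, distance or taxon comparisons.

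**Other tempting inferences.**
- Live starter in the control drink follows from the manufacturing text but is not stated outright. Shedding of starter organisms at Day 7 is not documented at all.
- Section 7.4 says "Participants who receive the control product will receive all identical interventions", but its parenthesis ties this to stool collection and follow-up. It is not evidence about yogurt exposure.

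**Conclusion.** The point holds in two parts, with different strength.

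- **Control label: a plain contradiction.** Sections 11.4.3 and 11.4.5 name a condition that none of the 300 children is in. This does not depend on whether the starter is live. Within-control change is the combined result of antibiotic and control yogurt, along with illness and time.
- **Recovery reading: not cleanly identified as planned.** BB-12 may be present in active-arm stool at Days 7, 14 and 21, and at Day 30 only under the conditions in the working. The resulting shift is unknown. It runs from negligible (Shannon at most about 0.005, Jensen-Shannon distance about 0.007-0.02) to material (about 0.03-0.12 and 0.07-0.20) under an assumed 100-fold depletion. The plan cannot tell which applies.

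The randomized comparison still estimates the effect of BB-12 added to yogurt in children on antibiotics. Aim 3 is secondary. The primary diarrhea comparison is unaffected, and no sample size or alpha changes.

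**What to change.** 1. **Wording.** In 11.4.3 and 11.4.5, call the control condition antibiotic plus control yogurt. Replace the antibiotic-only versus antibiotic-with-yogurt contrast with control yogurt versus BB-12 yogurt, and limit the randomized claim to the added effect of BB-12.
2. **Analysis.** Keep the unfiltered analysis in 11.4.2. Beside it, prespecify a sensitivity analysis of the between-arm diversity, distance and recovery contrasts with B. lactis reads removed and the remainder renormalized. Report B. lactis abundance separately as exposure, and mark any B. lactis finding from Metastats or LEfSe as product. Interpret Day 30 by last-dose date.
3. **Limit.** Do not remove the whole genus Bifidobacterium. Section 4.1.2 describes it as native, and a yogurt trial summarized in Section 4.1.5 counts its restoration as an effect, so removing it could erase a real result. If 16S cannot resolve B. lactis, say so and limit the recovery claim.

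**Cost.** Edits to two sections and one added pipeline step on existing data, with no new samples. The downside is that some native B. lactis reads are lost in the sensitivity analysis.
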